6.2.3. Baseline Definition

For this study, the patient begins study treatment on the day of hematopoietic stem cell transplantation (HSCT) defined as Day 0 in the protocol and study Day 1 for analysis. It is noted that the study schedule from the protocol refers to the reference date as Day 0. For reporting purposes, CDISC standards will be used, referring to the first day as Day 1.

If a patient received multiple HSCTs, the date of HSCT which occurred immediately before administration of BPX-501 will be considered study Day 1.

For all endpoints requiring a baseline reference, e.g., comparison with a post-baseline value, the baseline value will be the last non-missing result prior to HSCT.

6.2.4. Pooling Investigative Sites

The primary analysis will use data pooled across all investigative sites.

6.2.5. Examination of Subgroups

Subgroup analyses are intended for exploratory purposes to characterize the robustness of the primary and key secondary endpoints. Primary analysis subgroups include type of disease (malignant or non-malignant), and, potentially further subgroup analyses within these two major disease groups (e.g., ALL, AML, PID, hemoglobinopathies, etc.), highlighted below.

6.3. Subject Characteristics

Subject data will be displayed in subject listings and summarized in the appropriate analysis populations defined above.

6.3.1. Subject Disposition

Subject disposition will be presented for the appropriate analysis populations defined above. The following categories will be displayed in descriptive statistics summary tables:

- Subjects enrolled
- Subjects in the HSCT Safety Population (HSP)
- Subjects in the BPX-501 Safety Population (BSP)
- Subjects in the ITT (FAS) Population
- Subjects completed study (180-day follow-up)
- Subjects discontinued from the study early and reason of discontinuation.

6.3.2. Protocol Deviations

Protocol deviations will be identified as major or minor through data reviews by the Sponsor prior to database lock. Descriptive statistics will be summarized for subjects with major protocol deviations with respect to the relevant analysis population. The summary may be grouped into different categories of major violations such as:

- Violation of inclusion/exclusion criteria
- Non-compliance with study procedures
- Inappropriate intake of prohibited concomitant medications
- Missing essential study visit assessments

- Lost to follow-up
- Administrative decision of investigator or sponsor

Multiple deviations can occur in the same subject and thus a subject may be counted in more than one deviation category.

Major and minor protocol deviations will be presented in a subject data listing for all enrolled population, sorted by site.

6.3.3. Demographics and Background Baseline Characteristics

To further characterize the patient population at baseline, the following demographic and background characteristics will be summarized for the relevant analysis populations, stratified by type of disorder (malignant or non-malignant): demographics (age at enrollment, sex, and ethnicity), type of disease, prior HSCT (number of HSCT, type of HSCT), HLA typing, donor characteristics (age, ethnicity, relationship), conditioning regimen, and performance status (Lansky/Karnofsky score).

Demographic data will be presented in a listings and tables for the relevant analysis populations.

6.3.4. Treatment Exposure

Study treatment data including dose level of BPX-501 and rimiducid dosing (AP1903) information will be presented by type of disorder (malignant or non-malignant) and presented as patient data listings for the appropriate safety and ITT (FAS) populations.

Days on study will be calculated using the HSCT date as the reference date. The days on study for the date of interest will be calculated as (date of interest – date of HSCT + 1) for dates later than HSCT. For dates earlier than HSCT, the days on study will be calculated as (date of interest – date of HSCT).

Data listings will present study days in addition to assessment dates. Study day 1 is defined in section 6.2.3. For efficacy and safety endpoints the same rule for study day will apply.

6.3.5. Physical Examination

Physical examination of each subject's major body systems: general appearance, head/eyes/ears/nose/throat, neck, lungs, heart, abdomen, genitourinary, extremities, neurological, skin, and lymphatics and other. Results (normal, abnormal and clinically significant abnormal and not clinically significant) at screening visit will be tabulated for each body system with the number and percentage of subjects. The number and percentage of subjects in new or worsened conditions reported will be tabulated in the follow-up visits.

Physical examination results will be presented in a subject data listing, including the description of abnormalities observed by study visit.

Additional physical examination assessments are based on Karnofsky/Lansky performance status. The score for Karnofsky/Lansky performance status will be provided as patient listings by study visit.

6.3.6. Medical History

Pre-existing medical conditions are recorded in the medical history eCRF. Descriptive statistics including the number and percentage of subjects will be displayed for each medical condition.

Medical history data will be presented in patient listings for the safety populations.

6.3.7. Prior and Concomitant Medications

Following protocol specification and the schedule of assessments, concomitant medications are medications after BPX-501 infusion. Concomitant medication statistical summaries will include medications taken on or after the start date of BPX-501 infusion as well as medications that started prior to start date of BPX-501 infusion and continued after BPX-501 infusion. The following algorithm will be used to define prior and concomitant information:

- Prior medications: Any medications which started and ended before the date of BPX-501 infusion. If the start date of the medication is incomplete or missing, it will be treated as a prior medication.
- Concomitant medications: Any medications which start on or after the date of BPX-501 infusion as well as medications that started prior to date of BPX-501 infusion and continued after BPX-501 infusion.

All prior and concomitant medications recorded on the eCRF will be mapped to standardized terms using the World Health Organization Drug Dictionary (WHO DD) coding system. The Anatomical–Therapeutic–Chemical (ATC) classification level 2 and preferred term will be used to summarize the data overall and by disease type (malignant and non-malignant). A subject having the same medication more than once will be counted only once in the incidence table for that medication. For each ATC classification and preferred term, the number and percentage of subjects will be displayed. Separate prior and concomitant medication summary tables will be presented in the BPX safety population (BSP).

Additional subgroup concomitant medications tables will be summarized by usage context that may include: conditioning treatment, GvHD treatment, prophylaxis or infection treatment, and SAE treatment.

Prior and concomitant medications will be presented in a data listing with dose, units, frequency, route of administration, indication, start and end dates, and reason in the broader HSCT safety population (HSP).

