6.2.2. Missing Data and Handling of Dropouts

Unless otherwise specified, missing data will not be imputed for efficacy variables. For subjects who withdrew from the study prior to study completion, all data attained up to the point of discontinuation will be listed and included in data summaries. Patients will be censored at the time of their last documented study visit prior to or at the time of study withdrawal.

The term missing date refers to a completely missing date or to a partial date where month, day or year are missing. Unless otherwise stated, the handling of partial missingness of dates will impute using midpoint values. That is, missing days will be imputed as the 15th of the month and

missing months will be imputed as July 1st, unless a more suitable value can be imputed based on study or treatment start and end dates.

If an adverse event (AE) resolution date is completely missing, the duration (ongoing/resolved status) will be checked before imputing a date, noting when the AE started in relation to study treatments. If the ongoing flag is missing, then it is assumed that the AE is still present (i.e., do not impute a date).

Adverse event relationship missing: If the relationship for an adverse event is not recorded, it will be reported as missing in the presentation of listings and summaries of incidence results. Assessments of relatedness to AP1903/rimiducid should only apply for AEs which occur on or after the date of first rimiducid dose.

Adverse event severity missing: If the severity of an adverse event is missing, the severity will be assumed to be missing when summarizing data. Missing information will be reported as missing in the subject listings.

Non-study medication (concomitant medications, steroids) start and stop dates missing: If the start and/or stop dates of non-study medication use are incomplete or missing, the use will be assumed to be concomitant, unless the incomplete date information clearly indicates that the use stopped prior to the on-study-date. Missing or incomplete information will be reported as missing/incomplete in the subject listings.

For pharmacology and pharmacokinetic data, the following rules will be applied if there are values that are below the limit of quantitation (BLQ) or if there are missing values (e.g., no result [NR]) in a plasma concentration data series to be summarized.

- For the calculation of summary statistics, BLQ values will be set to zero.

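### SAP 6.2.2 and 6.3.7 class medications with a missing or partial start date in opposite ways, and the 6.3.7 sentence contradicts that section's own definitions

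*SAP*

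**What the plan says.** SAP 6.2.2 has a paragraph on medication dates, labelled "Non-study medication (concomitant medications, steroids) start and stop dates missing". Its rule is "If the start and/or stop dates of non-study medication use are incomplete or missing, the use will be assumed to be concomitant", with one exception: "unless the incomplete date information clearly indicates that the use stopped prior to the on-study-date". The SAP does not define that on-study date.

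SAP 6.3.7 gives the algorithm that separates prior from concomitant medications, with the BPX-501 infusion date as the dividing line. Prior is defined as "Any medications which started and ended before the date of BPX-501 infusion". The same bullet then adds, without any exception: "If the start date of the medication is incomplete or missing, it will be treated as a prior medication". Concomitant covers "Any medications which start on or after the date of BPX-501 infusion", and also drugs begun earlier and carried on past the infusion.

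SAP 6.2.2 also has a default for partial dates of any kind, which applies unless the SAP says otherwise: "missing days will be imputed as the 15th of the month", with a missing month set to 1 July. Whether it reaches medication dates is not said.

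Neither section refers to the other, and SAP 6.6 (changes from the protocol) does not take the matter up. Section 7.7 of the BP-404 protocol lists which medications to collect but gives no rule for incomplete dates. The BP-004 parent protocol is not among the documents. It could not settle the matter in any case, because the SAP introduction lets the SAP override the protocols where they differ, and both of these rules are in the SAP.

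**The concern.** One data condition, an incomplete or absent start date, leads to two different classes depending on which section the programmer reads. Both rules cannot be programmed. The choice would be made without documentation, at table-building stage, and it decides which of two tables a record enters.

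The 6.3.7 version raises a second problem. It assigns a drug to prior because part of its start date is missing, even where the part that was recorded shows the drug was given after infusion. Where it misplaces a drug that was used after infusion, the error always runs toward prior. The reported post-infusion use of steroids, other immunosuppressants and anti-infectives could then be too low. Those summaries are the background against which GvHD and the response to rimiducid are read.

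**Working it through.** No sample size, power or event count bears on this point, so the check is to apply each rule to the date patterns that can occur.

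**Inputs.** The 6.2.2 rule and its exception; the 6.3.7 sentence; the 6.3.7 definitions; the midpoint default in 6.2.2; the timing of HSCT and BPX-501 in SAP 6.2.3 and 4.1. I read the 6.2.2 exception as also covering a complete stop date.

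**Step 1: the rules side by side.** In every row the start date is missing or partial.

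| What else is known | 6.2.2 | 6.3.7 sentence | 6.3.7 definitions | Do the two rules agree? |
|---|---|---|---|---|
| 1. Stopped clearly before the on-study date | Not concomitant | Prior | Prior | Yes |
| 2. Stopped between HSCT and infusion (assuming on-study date = HSCT) | Concomitant | Prior | Prior | No |
| 3. Stopped after infusion | Concomitant | Prior | Concomitant, whatever the start date | No |
| 4. Stop date missing, or use ongoing | Concomitant | Prior | Concomitant if ongoing; undetermined if stop unknown | No |
| 5. Start month known and wholly after infusion | Concomitant | Prior | Concomitant | No |

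The rules disagree in 5 − 1 = 4 of the 5 patterns. That is a count of patterns, not a share of records.

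**Step 2: which rule is wrong.** Row 5 is the clear case. Suppose infusion is in March and a steroid is recorded as starting in May of the same year, day unknown. The drug cannot have started before infusion, yet the 6.3.7 sentence calls it prior. Midpoint imputation, if it applied, would give 15 May, which is also after infusion. In row 3, and in row 4 when use is ongoing, the start date is not needed: any drug used past the infusion is concomitant by definition, whether it began before or after. So the 6.3.7 sentence conflicts with the definitions beside it as well as with 6.2.2.

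**Step 3: the reference date.** SAP 6.2.3 starts study treatment at HSCT. SAP 4.1 gives BPX-501 at 14 ± 4 days, or 21 ± 14 days under some protocol versions:

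- 14 − 4 = 10 to 14 + 4 = 18 days
- 21 − 14 = 7 to 21 + 14 = 35 days

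If the on-study date is HSCT (an assumption, since the SAP does not say), the two anchors lie 7 to 35 days apart. In that window (row 2) it is 6.2.2 that departs from the 6.3.7 definitions. If the on-study date is the infusion date, row 2 merges into row 1. Either way, 6.2.2 needs its anchor stated.

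**Step 4: a gap next to the conflict.** When only the stop date is missing, 6.2.2 gives a rule and 6.3.7 gives none. That is not a contradiction, but a single rule should cover it.

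**Step 5: outputs that use the class.**

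- Directly: Tables 14.1.4.1 and 14.1.4.2; the usage-context tables in 6.3.7; the GvHD medication summaries in 6.4.2(iii).
- Possibly: Table 14.3.4.1.1, whose title refers to concomitant anti-infectives within 7 days. The SAP does not say that the 6.3.7 class filters it, and a 7-day match needs dates under either rule.
- Not directly: EFS (6.4.1), whose events are death, GvHD and Grade 4 infection; and infectious complications (6.4.3(v)), defined by the treatment an infection required, with no reference to the class.

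**The case against.** **The more specific section should prevail.** 6.3.7 is the section on medications, so its rule might be taken to override a general missing-data section. This does not stand. The 6.2.2 paragraph is itself specific to non-study medication, names steroids, and does not defer to any other section.

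**A programmer could read 6.3.7 sensibly.** An unknown start could be treated as a pre-infusion start, and the drug still classed as concomitant through the clause on drugs that carried on past infusion. This has force for rows 3 and 4, where misclassification is arguable rather than certain. It does not rescue row 5.

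**The consequences are small.** This stands. The affected outputs are descriptive, and SAP 6.5 rules out inferential testing of safety variables. A subject is counted once per medication, so one fully dated post-infusion record of the same drug keeps that subject in the concomitant table under either rule. The 6.3.7 listing shows start and end dates, and 6.2.2 has incomplete dates reported as such, so affected records stay visible.

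**Stronger readings that a reader might infer.** One is that every record with a partial start date changes table; row 1 shows otherwise. Another is that some percentage of records is misclassified; the documents give no rate of partial dates, and drugs that truly ended before infusion are correctly prior under 6.3.7. A third is that EFS or the infectious-complication results are compromised; neither definition uses the class.

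**Conclusion.** The contradiction is real and nothing in the documents resolves it. It is more than missing detail: taken literally, the 6.3.7 sentence gives a wrong class for a drug known to have started in a month after infusion, and arguably for one of unknown start that continued past infusion.

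The size is limited to descriptive medication outputs, and the number of records or subjects that would move cannot be derived. The conclusion rests on reading the 6.3.7 sentence literally. Row 2 alone also depends on taking HSCT as the on-study date. Wrong as written; low severity.

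**What to change.** Delete the 6.3.7 sentence on incomplete or missing start dates. State one rule in both 6.2.2 and 6.3.7, with the BPX-501 infusion date as the only reference date: a medication is prior only when the available parts of its start or stop date show that use ended before infusion; otherwise it is concomitant. Replace the undefined on-study date in 6.2.2 accordingly. State whether the midpoint imputation in 6.2.2 applies to medication dates and, if it does, whether it is applied before or after classification.

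The cost is one deleted sentence and a short edit to 6.2.2 before programming. The downside is an error in the other direction: some drugs given before infusion with no usable stop date, conditioning agents for example, may be counted as concomitant, so concomitant counts may be slightly higher. A table footnote giving the number of records classed by default would let the reader judge how much this matters.

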6.4. Efficacy Analysis

The analysis of primary and secondary endpoints will be based on the ITT (FAS) population as the primary analysis population. Any supportive sensitivity analyses may be assessed on the PP population or other subgroup defined below. Final decisions on different exploratory subgroups will be determined prior to the time of primary analysis.

6.4.1. Primary Efficacy Analysis

The primary efficacy endpoint is Event-Free Survival (EFS) up to 180 days using the ITT (FAS) population. Events corresponding to EFS outcome include

- Transplant-Related Mortality (TRM) for non-malignant patients or Non-Relapse Mortality (NRM) for malignant patients, defined as the time from transplant until death without evidence of recurrence or relapse,
- Severe GvHD, defined as any case of grade 3-4 acute GvHD regardless of organ involvement, any case of grade 2 acute GvHD with visceral (non-skin-only) organ involvement, or any case of moderate-severe chronic GvHD, and
- Life-threatening infections (Grade 4).

For patients with multiple events, the event that occurs first and the corresponding time will be used for the EFS. Subsequent EFS-qualifying events will be provided in a listing in order to describe longer-term outcomes observed in patients with a primary EFS event. Patients who do not experience an EFS-qualifying event will be censored on the last day of observation. EFS will be calculated from the date of HSCT transplant defined above.

Kaplan-Meier techniques will be used to estimate EFS at day 180. When estimable, additional summary statistics will include the median, minimum, maximum, the 25th and 75th percentiles of EFS along with the number of events and censored observations. Kaplan-Meier plots with descriptive summary statistics will be presented along with the number of patients at risk at various time points.

An additional sensitivity analysis of EFS may be performed using an expanded definition of EFS-qualifying events to include patients with skin-only grade 2 acute GvHD.

6.4.2. Secondary Efficacy Analyses

(i) Transplant-Related Mortality (TRM) for Non-Malignant patients or Non-Relapse Mortality (NRM) for Malignant patients at 100 and 180 days

This analysis is intended to characterize the contribution of Time-to-Transplant-Related Mortality (TRM) or Non-Relapse Mortality (NRM) to the composite EFS endpoint. TRM/NRM will be estimated using a Nelson-Aalen cumulative incidence function at days 100 and 180. An event for this endpoint is death without evidence of disease recurrence. Recurrence of disease or relapse will be considered a competing event. Cumulative incidence plots with descriptive summary statistics including incidence and 95% confidence intervals will be presented. If there is sufficient data, the analysis may be repeated by type of disease (malignant or non-malignant).

(ii) Cumulative Incidence and Severity of grade 2-4 acute organ GvHD and moderate - severe chronic GvHD at 180 days

This analysis is intended to characterize the contribution of acute or chronic GvHD to the composite EFS endpoint. Severity of acute and chronic GvHD will be summarized and further in the analysis of safety data. Cumulative incidence of GvHD at day 180 will be estimated from time of transplant using a Nelson-Aalen cumulative incidence function and treating death prior to GvHD as a competing risk.

Cumulative incidence plots with descriptive summary statistics including incidence and 95% confidence intervals will be presented. If there is sufficient data, the analysis will be repeated for each type of disorder (malignant or non-malignant) stratification.

Depending on the number of events, additional GvHD severity subgroups to be analysed include acute grade 1-4 GvHD, grade 2-4 GvHD including skin-only presentation, grade 3-4 GvHD, mild-severe chronic GvHD, and, severe chronic GvHD. The same statistical methods and summary statistics described above will be applied to these analyses.

(iii) Time to Resolution of Acute or Chronic GvHD After Administration of Rimiducid (including Response to Rimiducid)

The resolution of acute GvHD (aGvHD) or chronic GvHD (cGvHD) after administration of rimiducid will be based on the response grading of the GvHD criteria provided in the protocol. The event for this endpoint is any patient who achieved a best overall response (BOR, i.e., either a Complete Response (CR) or Partial Response (PR)) based on aGvHD grading. Only patients experiencing aGVHD who received rimiducid (AP1903) infusion for treatment will be considered for this endpoint. Best overall resolution of aGVHD is defined from the date of AP1903 infusion. The percentage of patients with acute or chronic GvHD, the number of doses of rimiducid, and the best overall response to rimiducid within 7 and 30 days will be presented in listings and summarized. Concomitant medication usage in subjects with acute or chronic GvHD and, further, among those subjects who went on to receive rimiducid, will also be summarized.

Additional analysis and summary statistics will be conducted for resolution of chronic GvHD after administration of rimiducid as well as any case of GvHD (acute or chronic).

(iv) Immune reconstitution as determined by T cell subset counts at day 180

- a. Median and range of CD3 counts at 30, 60, 100 and 180 days
- b. Median and range of CD4 counts at 30, 60, 100 and 180 days
- c. Median and range of CD8 counts at 30, 60, 100 and 180 days

Quantitative assessment of each immune T-cell counts will be performed at various visit time points after transplant as captured in clinical database up to day 180 of follow-up. Analysis and statistical summaries will be performed separately for each T cell subtype assessed. The pattern of each immune reconstitution lab counts will be summarized using graphical summaries and descriptive statistic summary tables including mean (standard deviation), median, and range (minimum, maximum) across the time points assessed. Plots of mean and median cell counts representing measurements over time will be generated to visualize general patterns over time of immune reconstitution.

Additional cell types and analytes for quantitative immunophenotyping include the absolute and relative numbers of CD3+CD19+ T cells (containing iC9), as well as the number of B cells, NK cells, and levels of IgA, IgM and IgG. In order to describe the pharmacodynamic effects of BPX-501 via proliferation of CD3+CD19+ cells, values post-rimiducid may be excluded. A separate analysis will examine CD3+CD19+ levels using the most recent samples available before and after treatment with rimiducid.

(v) *Time to immune reconstitution defined by CD3 count > 500 cells/uL; CD4 > 200 cells/uL or CD8 count of 200 cells/uL*

Time to immune reconstitution will be based on CD3, CD4 or CD8 counts for the defined thresholds above. Events are defined from the time of transplant to the time at which the threshold is achieved, with death considered as competing event. A patient not achieving the threshold T cell count will be censored on the last recorded visit day.

Time to immune reconstitution will be estimated using a Nelson-Aalen cumulative incidence function for each T cell subtype. Parameters estimates will be summarized for all subjects and by disease type (malignant or non-malignant). When estimable, additional summary statistics will include the median, minimum, maximum, the 25th and 75th percentiles of immune reconstitution, along with the number of events and censored observations. A cumulative incidence plot with descriptive summary statistics will be presented along with the number of patients at risk at various time points.

(vi) *Disease-Free/chronic GvHD-Free survival at 180 days*

The disease-free/chronic GvHD-free survival endpoint at 180 days will be assessed on the ITT (FAS) population. Events corresponding to disease-free/chronic GvHD-free survival outcomes include chronic GvHD, disease relapse for malignant subjects, disease recurrence for non-malignant subjects, or death by any cause. For patients with multiple events, the event that occurs first and the corresponding time will be used. Patients who do not experience an event will be censored on the last recorded visit day. Each patient outcome duration will be calculated from the date of transplant.

Kaplan-Meier techniques will be used to estimate disease-free/chronic GvHD-free survival at day 180. When estimable, additional summary statistics will include the median, minimum, maximum, the 25th and 75th percentiles along with the number of events and censored observations. Kaplan-Meier plots with descriptive summary statistics will be presented along with the number of patients at risk at various time points.

(vii) *Disease status for the following diseases at 180 days:*

- a. Primary immune disorders as determined by CD3 T cell count \geq 500 cells/uL and normal levels of IgA and IgM at 180 days
- b. Haemoglobinopathies as determined by incidence of RBC transfusion independence (TI) and untransfused haemoglobin of \geq 8.5 g/dL at 180 days
Transfusion Independence (TI) is defined as not having received packed red blood cell transfusions for the previous 8 weeks.
- c. Fanconi Anemia as determined by RBC \geq 3,000,000 cells/uL, neutrophil count \geq 1500 cells/uL and platelet count \geq 150,000 at 180 days
- d. Leukemia as determined by relapse-free-survival (RFS) at 180 days

For a)-d) above, cumulative incidence or survival will be assessed within the patient subpopulation defined as having those diseases at baseline. Cumulative incidence events for a.)-c.) are defined from the time of transplant until the event criteria described is achieved. Competing risks for a.)-c.) include any non-recurrence mortality. Events for RFS are defined as time to relapse or death from any cause.

Cumulative incidence for a.)-c.) will be estimated using a Nelson-Aalen cumulative incidence function for each disease subtype. When estimable, additional summary statistics will include the median, minimum, maximum, the 25th and 75th percentiles of immune reconstitution, along with the number of events and censored observations. A cumulative incidence plot with descriptive summary statistics will be presented along with the number of patients at risk various time points.

Kaplan-Meier techniques will be used to estimate RFS in subjects with leukemia. When estimable, additional summary statistics will include the median, minimum, maximum, the 25th and 75th percentiles along with the number of events and censored observations. Kaplan-Meier plots with descriptive summary statistics will be presented along with the number of patients at risk at various time points.

6.4.3. Other Efficacy Analyses:

(i) Time to Relapse in Subjects with Leukemia

Cumulative incidence of acute leukemia relapse will be estimated from time of transplant using a Nelson-Aalen cumulative incidence function and treating death prior to relapse as a competing risk. Cumulative incidence plots with descriptive summary statistics including incidence and 95% confidence intervals will be presented.

(ii) Time to Neutrophil Engraftment

Events for neutrophil engraftment is defined as the first of three consecutive measurements of an ANC $\geq 500/\mu\text{L}$ following the conditioning regimen induced nadir, starting from Day 0 (day of transplant). A patient that does not achieve the count of ANC $\geq 500/\mu\text{L}$ will be censored at the last assessment date.

Time to neutrophil engraftment will be estimated using a Nelson-Aalen cumulative incidence function. Death will be considered a competing event. Cumulative incidence plots with descriptive summary statistics including median engraftment time and 95% confidence intervals will be presented.

(iii) Time to Platelet Engraftment

Events for platelet engraftment is defined as the first of three consecutive measurements of platelet count $\geq 20,000/\mu\text{L}$ without platelet transfusion support for seven days. A patient that does not achieve the threshold platelet count of $\geq 20,000/\mu\text{L}$ as required will be censored at the last assessment date.

Time to platelet engraftment will be estimated using a Nelson-Aalen cumulative incidence function. Death will be considered a competing event. Cumulative incidence plots with descriptive summary statistics including median engraftment time and 95% confidence intervals will be presented.

(iv) Analysis of Primary and Secondary Graft Failure

Primary graft failure is defined as failure to achieve an absolute ANC ≥ 500 cells/ μ L by Day 30. The proportion of patients experiencing primary graft failure in the first 30 days will be summarized and reported with a 95% confidence interval.

Secondary graft failure is defined as initial neutrophil engraftment followed by a subsequent decline in neutrophil counts to < 500 cells/ μ L which is unresponsive to growth factor therapy. Sustained neutropenia, i.e., neutrophil counts to < 500 cells/ μ L, observed for greater than 30 days from the administration of growth factors will be summarized.

(v) Infectious Complications

Infectious complications are defined as clinically significant viral reactivations, viral infections requiring antiviral treatment, bacterial and fungal infections requiring the use of non-prophylactic antibiotics and antifungals, and rehospitalizations due to viral infection. Each of these occurrences will be summarized in tables and listings.

